**Combined Bleaching Technique: Efficacy and Tooth Sensitivity - A Randomized,
Double Blind Clinical Trial**

ClinicalTrials.gov ID: NCT03089216

May 1, 2018

Objective

This study evaluated the efficacy, color stabilization, and tooth sensitivity (TS) during and after the use of a combined bleaching technique, varying the application time of 35% hydrogen peroxide (HP) and the use of a desensitizing dentifrice containing arginine (ARG).

Study design

This is a randomized controlled clinical trial, parallel and double blinded, with a similar allocation rate between groups, registered at clinicaltrials.gov under the identification number NCT03089216. The study has been conducting at the School of Dentistry of the Federal University of Goias (UFG), following CONSORT statement, after the approval of the Ethics Committee of the Federal University of Goias, Brazil (CAAE: 52047115.2.0000.5083).

One hundred and eight participants were randomly assigned to 4 groups ($n = 27$): OFF40 (without ARG): two 20-minute HP applications (2x20); D-OFF40 (with ARG): two 20-minute applications (2x20); OFF20 (without ARG): one 20-minute HP application (1x20); and D-OFF20 (with ARG): one 20-minute HP application (1x20). In all groups, at-home bleaching was performed with 10% carbamide peroxide (CP) for two hours daily for 16 days. Color evaluations were performed before bleaching and at 5, 8, 12, and 16 days from the beginning of the procedure, and 7 and 30 days after the end of the treatment, with VITA Classical and VITA Bleachedguide 3D-MASTER shade guides (Δ SGU) and a digital spectrophotometer, VITA Easyshade (VITA Zahnfabrik). The TS evaluation was performed with a visual analogue scale (0-10) and numerical scale (0-4) in different periods.

Statistical Analysis Plan

Statistical analyses will be performed using SPSS 20.0 (SPSS Inc., Chicago, IL, USA) with $\alpha = 0.05$. The means of the SGU at baseline and after different assessments will be calculated for each group. In order to evaluate whether the bleaching therapies were effective or not, the data from the SGUs will be analyzed using the Kruskal-Wallis and Mann-Whitney tests for between-group comparisons,

and the Friedman and Wilcoxon tests with Bonferroni correction ($\alpha = 0.002$) for within-group comparisons. The ΔE values will be submitted to two-way analysis of variance (ANOVA).

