The Tooth Sensitivity intensity will be analyzed using Kruskal- among-group comparisons within each evaluation time (baseline, immediately after the in-office bleaching, daily during the at-home bleaching, and up to 48 hours after the treatment). The comparisons among the assessment times within each group will be performed using the Friedman and Wilcoxon tests with Bonferroni correction ($\alpha = 0.008$).

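### Baseline tooth sensitivity and pre-bleaching colour are collected but not used as covariates in the between-arm analyses, and baseline sensitivity is tested between randomised arms

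*Combined protocol and SAP*

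**What the plan says.** The Study design section describes the trial thus: "This is a randomized controlled clinical trial, parallel and double blinded, with a similar allocation rate between groups". It has 108 participants in four arms of 27, which differ in hydrogen peroxide application time and in use of the arginine dentifrice. TS is scored on two scales, a visual analogue scale (0-10) and a numerical scale (0-4).

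The TS paragraph of the Statistical Analysis Plan section sets out "among-group comparisons within each evaluation time (baseline, immediately after the in-office bleaching", then each day of the at-home phase and on to 48 hours after treatment), using a Kruskal-type rank test whose name is cut off in the text. No change score, covariate or stratum is named. Baseline TS otherwise enters only the comparisons of times within each group (Friedman and Wilcoxon, α = 0.008), and these do not compare arms.

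For instrument-measured colour, the same section says: "The ΔE values will be submitted to two-way analysis of variance (ANOVA"). It names no covariate, does not define ΔE and does not name the two factors. The baseline readings exist: "Color evaluations were performed before bleaching", with the shade guides and the spectrophotometer, and then at six later times.

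**The concern.** The Objective asks about application time and the dentifrice, and both are between-arm questions. A baseline reading of the same outcome is often the best available predictor of the later reading. Here it costs nothing further to obtain, yet no between-arm analysis is said to adjust for it. A participant who arrives with a TS score of 3 and still scores 3 is ranked exactly like one who arrives at 0 and is brought to 3 by bleaching. Variation present before treatment therefore stays in the comparison as noise, and chance imbalance between arms of 27 is not corrected.

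Baseline TS is instead put through a significance test between arms. Under proper randomisation the null hypothesis is true by design, so a small p-value is a false alarm. A large one is no evidence that the arms are balanced enough to ignore baseline.

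**Working it through.** **Plan's own figures.** The SAP gives no effect size, SD or power, so the sample size cannot be reproduced beyond 108/4 = 27. The two Bonferroni thresholds can be:

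- TS: four assessment occasions (baseline, after in-office, at-home, 48 hours) give 4 × 3/2 = 6 pairs, and 0.05/6 = 0.0083, stated as 0.008. This counts the at-home period as one occasion, which is an inference.
- Shade guide units: seven colour readings give 7 × 6/2 = 21 pairs, and 0.05/21 = 0.0024, stated as 0.002.

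Both agree. They show that baseline readings are meant to be used, but only within groups.

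**The baseline test.** The false-positive rate is nominally 5% per scale. For two scales it is 1 − 0.95² = 9.75% if they were independent; both measure TS, so 9.75% is better read as an upper figure. With four arms of 27 and mostly zero scores, simulation gave about 4%. If every baseline score were 0, the rank statistic would be undefined.

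**Later TS scores.** Let rho be the correlation between the baseline and later score. It is not in the documents, so 0.3, 0.5 and 0.7 are assumed. Adjusting for baseline multiplies the variance of a between-arm contrast by 1 − rho². The equivalent unadjusted arm size is 27/(1 − rho²).

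| rho | 1 − rho² | Equivalent per arm |
|---|---|---|
| 0.3 | 0.91 | 29.7 |
| 0.5 | 0.75 | 36.0 |
| 0.7 | 0.51 | 52.9 |

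The formula is for a continuous outcome, so it is only a guide for ranked ordinal scores. If nearly all baseline scores are 0, rho is near 0, the factor is near 1 and nothing is gained.

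**ΔE.** If ΔE is a distance from the pre-bleaching reading, the comparator is an unadjusted change and not a raw follow-up score. For a simple signed change with equal variance at both times, the variance factors relative to a raw score are 2(1 − rho) unadjusted and 1 − rho² with baseline as covariate. Their ratio is (1 + rho)/2.

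| rho | 2(1 − rho) | 1 − rho² | Ratio (1 + rho)/2 |
|---|---|---|---|
| 0.3 | 1.40 | 0.91 | 0.65 |
| 0.5 | 1.00 | 0.75 | 0.75 |
| 0.7 | 0.60 | 0.51 | 0.85 |

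The gain shrinks as rho rises, the reverse of the TS pattern, because subtracting baseline already does most of the work when rho is high. ΔE is an unsigned colour distance, so these figures are only indicative.

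**Cost in the ΔE model.** Suppose the factors are application time and dentifrice, with one ΔE per participant. The residual degrees of freedom are 108 − 4 = 104, or 101 with three colour coordinates as covariates.

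**The case against.** The strongest reply is that nothing here is wrong. Randomisation balances participants with existing sensitivity in expectation, so unadjusted tests at later times keep their error rate and are unbiased. That stands: adjustment is a choice made for precision.

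The baseline test also does little harm. No correction across times is stated for the among-group tests, so it uses up no shared allowance, and nothing in the plan depends on its result. Dropping it alters no threshold and no treatment estimate. That stands too.

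Three stronger readings are tempting, and the documents do not support them:

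- **The ΔE analysis ignores baseline.** ΔE is a difference between two readings, most naturally from the one before bleaching, so baseline is already part of the outcome. What can be said is that its reference is not stated and that baseline colour is not a covariate.
- **A large power gain is being given up.** For an assumed 0.5-SD effect, a pooled 54 v 54 t-test would have power of 73% unadjusted and 77%, 84% and 95% adjusted at rho 0.3, 0.5 and 0.7. The 0.5 SD is not in the documents, the pooled t-test is not the planned TS rank test, and the factor 1 − rho² is the wrong comparator for a change-type ΔE.
- **The TS results will contain noise that could be removed.** The documents give no distribution of baseline TS. If participants almost all start at 0, there is nothing to remove.

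**Conclusion.** The point holds as a modest improvement in precision, with no error or bias in the planned tests. The later among-group TS comparisons and the ΔE ANOVA name no baseline adjustment although the values are collected, and the between-arm test of baseline TS cannot inform about treatment.

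The size is uncertain because rho is assumed throughout. The variance reduction is 9% to 49% for later TS scores at rho 0.3 to 0.7, falling to nothing if baseline TS is almost all zero. For ΔE it is 35% down to 15% over the same range, on the rough assumption that ΔE behaves like a simple change from the pre-bleaching reading with equal variances. Removing the baseline test on its own would change no treatment result; the adjustment is what gives the point its value.

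**What to change.** 1. Take baseline out of the among-group TS tests and report baseline TS on both scales descriptively by arm.
2. For later TS, prespecify a baseline-adjusted rank comparison of arms, to be used if baseline TS varies. Either a rank ANCOVA with baseline TS as covariate, or a van Elteren test stratified by baseline zero v above zero, would serve. The van Elteren test compares two groups, so comparing all four arms at once needs its stratified Kruskal-Wallis extension. Judge whether baseline TS varies on all arms pooled, before any comparison by arm.
3. State that ΔE is measured from the pre-bleaching reading and name the two ANOVA factors. Then add the pre-bleaching spectrophotometer colour values as covariates.

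The change is to SAP wording only and needs no new measurements, assuming the spectrophotometer's component colour values were kept along with ΔE. The statistical cost is up to three degrees of freedom in the ΔE model. The wording should be settled before outcomes are seen by arm.
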